This clinical trial will help clarify the role of multi-ingredient supplements containing amino acids, vitamins, and minerals in the prevention and management of CVD and CVD risk factors.

RESEARCH OBJECTIVES

The overall objective of this study is to determine whether daily supplementation with the dietary supplement Cardioflex for 90 days will reduce risk factor biomarkers for CVD in adults aged 30–65 years old.

The primary objective is to determine whether daily supplementation with the dietary supplement Cardioflex will improve their plasma lipid profile (total cholesterol, HDL-cholesterol, LDL-cholesterol, triglycerides, lipoprotein A).

The secondary objectives are to determine if Cardioflex supplementation will improve anthropometric measures (waist circumference, body mass index), cardiac measures (heart rate, heart rate variability, accelerated plethysmography (APG age, which measures the biological age of arteries), blood pressure), and inflammatory and endothelial function biomarkers (C-reactive protein, IL-6, sICAM-1, sVCAM-1,) and assess the safety of the supplement by measuring serum levels of liver and kidney enzymes (alanine transaminase; ALT, aspartate transaminase; AST, lactate dehydrogenase; LHD, blood urea nitrogen; BUN, and creatinine). To quantify confounding variables, participants were asked to record everything they ate and drank in a food log and wore a pedometer to

track total steps on day 1 (beginning), day 45 (mid-point) and day 90 (end) of the study.

HYPOTHESES

- Participants who consume one serving (10 g) of Cardioflex per day, the label recommended dosage, will have improved lipid profile, as reflected by lower levels of total cholesterol, LDL-cholesterol, triglycerides, and lipoprotein A, and higher HDL-cholesterol than participants who consumed the placebo.
- Participants who consume one serving of Cardioflex per day will have improved cardiac health, as measured by lower blood pressure, higher HRV, lower APG age, and lower levels of inflammation biomarkers (C-reactive protein, IL-6, sICAM-1, and sVCAM-1) than participants who consumed the placebo.
- No significant changes will be seen in anthropometric measures (waist circumference, body mass index) or liver and kidney functions biomarkers (ALT, AST, LHD, BUN or creatinine) between the Cardioflex and the placebo group.

STUDY DESIGN

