A sample size calculation was completed using a standard sample size in equation 1 to determine the number of participants needed for the study. With $\alpha = .05$ and $\beta = .90$ and a 12% mean decrease of cholesterol using previously published data (Hobbs et al., 2014) in the supplementation group, we calculated that we would need 60 subjects to reach statistical significance. With an expected attrition rate of 20%, we determined that 72 participants needed to be recruited.

$$n = \frac{2(Z_{\alpha} + Z_{1-\beta})^2 \sigma^2}{\Delta^2}$$

Equation 1 - Estimated sample size equation

Z_{α} = constant to the accepted error, $Z_{1-\beta}$ = constant according to power, σ = standard deviation, Δ = effect size

Overall, 90 adults were screened for eligibility, with 75 adults being deemed eligible. At the time of starting the study 69 adults chose to participate, and 6 eligible adults chose not to participate for personal reasons not related to the study.

STUDY PROCEDURES AND ASSESSMENTS

BLOOD COLLECTION

Blood was drawn at 3 time points in the study – the assessment for eligibility for entry into the study, baseline, and end of the 90-day supplement period. All blood samples were collected in the morning after at least 8 hours overnight fast. The participants reported to the RCFFN at the University of Manitoba Ft. Garry Campus. Blood samples were taken by venipuncture from an antecubital vein into serum tubes by a certified phlebotomist. For eligibility assessment, one 5mL serum tube was withdrawn. For clinical trial baseline and endpoint measurements, two 10mL serum tubes, and one 5mL serum tube, totaling 25mL of blood was withdrawn from each participant. Samples were centrifuged at 4100g for 10 minutes. The plasma was allocated into Eppendorf tubes and frozen at -86 ° C for later analysis.

Cardiac Measurements

Participants were required to sit for a minimum of 5 minutes rest at the beginning of each assessment session. Blood pressure was measured at the brachial artery of the left arm, using an automatic sphygmomanometer (Series 10, Omron). The blood pressure of each participant was taken three times, and the average was recorded. Accelerated plethysmograph (APG) type, HR, and HRV were assessed using a Meridian digital pulse-wave analyzer (DPA) machine (Long Life Cardio LLC, USA). HRV was measured using the standard deviation of all of the RR intervals (the distance between each heartbeat) after 5 minutes of recording.

ANTHROPOMETRICS

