Data were analyzed using IBM SPSS Statistics (v.25). Significance was determined using the treatment effect between groups. The significance value was set at $p \leq 0.05$. An independent t-test showed that there were no statistical differences between the starting points of the two groups ($P > 0.05$), indicating that the two groups were indistinguishable from each other.

The primary analysis was conducted using the post-treatment biomarker value, comparing the two groups, and controlling for their baseline values by using analysis of covariance. Analysis of covariance examines the differences in the mean values of the dependent variable that is related to the effect of the controlled independent variable while taking into account the influence of the uncontrolled variables. In this study, the dependent variable was the biomarkers being tested, the controlled independent variable was the treatment given and the uncontrolled variables were the baseline differences between participants. Analysis of covariance makes the assumption that the data is normally distributed in equal variances. To check the assumption of normal distribution, a Shapiro–Wilk test was performed. To check the assumption of equal variance, a Levene's test was performed.

Results are given as mean \pm standard deviation (SD). Outliers were determined as values greater or less than the mean \pm 3*SD (Jones, 2019). If outliers were present, they were removed, and the results were recalculated. For each parameter, the percent change was calculated by equation 3.

$$\% \text{ Change} = \frac{\text{Final Value} - \text{Starting Value}}{\text{Starting Value}} \times 100$$

Equation 3: Percent change calculation

REFERENCES

- Benjamin, E. J., Muntner, P., Alonso, A., Bittencourt, M. S., Callaway, C. W., Carson, A. P., . . . Stroke Statistics, S. (2019). Heart Disease and Stroke Statistics-2019 Update: A Report From the American Heart Association. *Circulation, 139*(10), e56-e528. doi:10.1161/CIR.0000000000000659
- Black, A. E. (2000). Critical evaluation of energy intake using the Goldberg cut-off for energy intake:basal metabolic rate. A practical guide to its calculation, use and limitations. *Int J Obes Relat Metab Disord, 24*(9), 1119-1130. doi:10.1038/sj.ijo.0801376
- Canada, S. (2020). Table 13-10-0801-01 Leading causes of death, total population. Retrieved from <https://www150.statcan.gc.ca/t1/tb11/en/tv.action?pid=1310080101>

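### The only criterion attached to the safety objective is a non-significant difference in liver and kidney markers, which without a margin does not show absence of harm

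*Combined protocol and SAP*

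**What the plan says.** All references are to the combined protocol and SAP.

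- **Research Objectives.** One secondary objective is to "assess the safety of the supplement by measuring serum levels of liver and kidney enzymes". The markers are ALT, AST, LDH, BUN and creatinine.
- **Hypotheses, third item.** "No significant changes will be seen in anthropometric measures (waist circumference, body mass index) or liver and kidney functions biomarkers", comparing Cardioflex with placebo.
- **Statistical Analysis.** "Significance was determined using the treatment effect between groups", and "The significance value was set at" p ≤ 0.05. The model is an analysis of covariance on the post-treatment value, adjusted for baseline. Values more than 3 SD from the mean are removed and the results recalculated. Safety markers are not excepted.
- **Sample Size.** The size rests on a "12% mean decrease of cholesterol using previously published data", and "we calculated that we would need 60 subjects to reach statistical significance".

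For the safety markers the plan gives no margin, equivalence or non-inferiority test, confidence-interval rule, threshold for individual abnormal values, standard deviation or power.

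**The concern.** The third hypothesis predicts a null result, so failing to reject the null appears to confirm it. That outcome becomes more likely as the trial gets smaller or noisier, which is the wrong direction for a safety claim. The trial was sized for a cholesterol effect, so nothing in the plan says how large a rise in ALT or creatinine it could rule out. A comparison of group means can also hide a few individuals with abnormal values, and the outlier rule may remove those individuals from the comparison altogether.

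Safety is not incidental here. The Study Design section gives the lack of evidence on effectiveness and safety as the reason for running the trial. A report that the markers did not change significantly would be read as an answer to that question.

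**Working it through.** **1. The plan's own figure.** The 60 subjects cannot be reproduced, because the plan defines the symbol ("σ = standard deviation, Δ = effect size") but gives no value for σ. Working backwards with two-sided α = 0.05 and power 0.90 (the plan writes β = .90, read here as power):

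d = (1.960 + 1.282) × √(2/n per arm)

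- 60 in total (30 per arm): d = 0.84, which implies an SD of 12/0.837 = 14.3% of the mean.
- 60 per arm: d = 0.59, SD about 20.3%.

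I read 60 as the total, because 72 is the total to be recruited. On that reading the trial was sized for a large standardized effect on cholesterol. It was not sized for any safety marker.

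**2. Inputs for the safety markers.** From the plan: about 60 evaluable, significance level 0.05, baseline-adjusted ANCOVA. Assumed because not stated: 1:1 allocation, a two-sided test, baseline-to-final correlation r from 0 to 0.8, and rises expressed in SD units.

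**3. Chance of missing a true rise in one marker.** For a rise of d SD, the noncentrality is d / (√(1 − r²) × √(2/30)), with √(2/30) = 0.258, 57 degrees of freedom and critical t = 2.002. The miss rate is one minus the noncentral-t power. The 95% CI half-width is 2.002 × 0.258 × √(1 − r²).

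| r | 0.3 SD rise missed | 0.5 SD rise missed | CI half-width (SD) |
|---|---|---|---|
| 0 | 79% | 52% | 0.52 |
| 0.5 | 74% | 41% | 0.45 |
| 0.7 | 64% | 24% | 0.37 |
| 0.8 | 52% | 11% | 0.31 |

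**4. Sensitivity to numbers analysed.** If all 69 starters were analysed, a 0.3 SD rise is missed in 77%, 71%, 60% and 47% at the same four correlations. With 20% attrition from 69 (69 × 0.8 ≈ 55, about 28 per arm) the figures are 80%, 75%, 66% and 55%.

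**5. Five markers together.** The hypothesis covers five safety markers, and one significant result would contradict it. If all five truly rose by 0.3 SD at r = 0.5, all would be missed in between 0.739⁵ = 22% of trials (markers independent) and 74% (perfectly correlated). The table therefore describes a rise in a single marker.

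**6. Outlier rule.** The largest possible distance of one value from its own sample mean is (n − 1)/√n SDs. For n = 30 that is 29/√30 = 5.3. The 3 SD rule can therefore take effect in an arm of this size, and a markedly raised enzyme is the kind of value it would remove.

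**The case against.** The strongest reply is that the plan never says p > 0.05 means safe. The objective is to assess safety by measuring the markers. The third hypothesis is a prediction that also covers waist circumference and BMI. The list of dependent variables under Study Design omits the liver and kidney markers, although Blood Analysis says they were measured. Applying the ANCOVA to them is therefore an inference. This is fair as far as it goes. Still, no other criterion is linked to the safety objective, so anyone following the plan has only significance to work with.

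A reader might also infer that the trial would usually miss any modest rise, or that its design cannot support a safety conclusion at all. The documents do not support either reading. The planned ANCOVA detects a 0.5 SD rise in 59%, 76% and 89% of trials at r = 0.5, 0.7 and 0.8. If there is truly no difference, 30 per arm would exclude a 0.5 SD rise with probability 61%, 77% and 90% at those correlations (one-sided 0.025, normal approximation). For a 0.3 SD rise the probabilities are 27%, 37% and 49%. Whether that is enough depends on a margin and a correlation that the documents do not give. Without SDs, none of these rises can be translated into laboratory units.

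The plan does report means and SDs, so a reader who knows the arm sizes could derive an unadjusted interval. That does not supply the adjusted interval, a limit to set it against, or the individual values.

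**Conclusion.** The point stands as a fault of inference and reporting. With no margin, a non-significant difference does not show absence of harm; this is true whatever SD, correlation or sample size is assumed.

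The size of the problem does depend on assumptions: 30 per arm, 1:1 allocation, a two-sided 0.05 test and one marker at a time. A rise of about 0.3 SD or less is missed more often than not at every correlation tried. At 0.5 SD that is true only near zero correlation. The outlier rule aggravates the problem, by an amount that cannot be computed from the documents.

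The sponsor should correct this. The primary lipid analysis is unaffected, but a stated secondary objective cannot be answered by the criterion as written.

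**What to change.** 1. Reword the third hypothesis so that non-significance is not taken as evidence of safety.
2. For each of the five markers, report the baseline-adjusted difference between arms with its 95% CI, and state the largest rise not excluded.
3. Tabulate, per arm, the participants who move from within to above the laboratory's upper reference limit.
4. Exempt the safety markers from the 3 SD removal, in both the intervals and the counts.
5. If the interval is to be compared with a limit for each marker, set and justify that limit before unblinding. The document is written in the past tense, so unblinding may already have happened; in that case label the limit post hoc. Otherwise, conclude that no signal was detected and that rises up to the upper interval bound are not excluded.

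No new participants or samples are needed; the cost is rewording and a small table. The downside is that the safety conclusion becomes less favourable and some markers will read as inconclusive.

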Although direct comparisons between multi-ingredient supplements and single ingredients have never been done, a substantial body of evidence suggests that multi-ingredient formulations greatly increase the efficacy of the product (Harty et al., 2018). For example, there is research to suggest that multi-ingredient supplements can improve lipid blood profiles in as little as 30 days (Hobbs, Caso, McMahon, & Nymark, 2014). However, the body of literature evaluating dietary supplements to reduce CVD prevalence and prognosis is minimal. The view by most health care practitioners and government agencies is that currently there is insufficient data to recommend the routine use of nutrient supplements to prevent or treat CVD. It is only in the last decade that dietary supplement databases with open access for the public have existed in the USA (Coates, 2016). Although a great deal of progress has been made in recent years, much remains to be done to ensure that dietary supplements are safe, efficacious, and reasonable in cost

so that they contribute positively to the public's health. Given the potential benefit of these products, more research needs to be done.

Cardioflex is a multi-ingredient supplement comprised of amino acids (L-lysine, L-proline, L-glutamine, L-threonine), vitamins (vitamins A, C, E, folate, vitamin B12), minerals (potassium, magnesium, selenium) and CoQ10. The individual ingredients in Cardioflex have shown or been hypothesized to show, positive results in reducing CVD and CVD risk factors. For example, the literature demonstrates that amino acids can play a significant role in cardiovascular health. L-threonine supplementation has been shown to lower blood pressure in patients with CVD (Tuttle, Milton, Packard, Shuler, & Short, 2012). High antioxidant intake has been shown to prevent atherosclerosis (Nunez-Cordoba & Martinez-Gonzalez, 2011). Low blood serum levels of magnesium have been associated with an increased risk for several chronic diseases including diabetes, hypertension, coronary heart disease, and osteoporosis (Kass, Weekes, & Carpenter, 2012). Multiple randomized, placebo-controlled, clinical trials show that daily supplementation of CoQ10 can cause significant antihypertensive effects in as little as 4 weeks of treatment (Ho, Bellusci, & Wright, 2009).

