To determine the effects of Cardioflex on CVD risk, the dependent variables tested included anthropometrics (weight, height, waist circumference), cardiovascular parameters (blood pressure, heart rate, HRV, APG age), dietary intake, plasma lipid profile (total cholesterol, HDL-cholesterol, LDL-cholesterol, triglycerides, lipoprotein A), and inflammatory and endothelial function biomarkers (C-reactive protein, IL-6, sICAM-1, sVCAM-1). Anthropometrics were included because large scale epidemiological studies have shown correlations between CVD mortality and BMI (Valavanis, Mougiakakou, Grimaldi, & Nikita, 2010) and increased waist circumference is recognized as a major cardiometabolic risk factor (Tchernof & Despres, 2013). Cardiovascular parameters carry valuable information for the prediction of long-term and near-term CVD risk. Blood

pressure is a consistent risk factor for the development of atherosclerosis (Lu, Cassis, & Daugherty, 2007). A higher resting heart rate is linked with greater CVD risk (Fox et al., 2007). Reduced HRV is associated with an increased risk for coronary heart disease and CVD mortality (Liao et al., 1997). Arterial elasticity is an established risk factor to predict future CVD events (Glasser et al., 1997). Lipid profile is recognized as an established risk factor in the development and progression of CVD (Graham, Cooney, Bradley, Dudina, & Reiner, 2012; Jellinger et al., 2012). Inflammation and endothelial function play a significant role in developing atherosclerosis, and risk of future cardiovascular events (Jarvisalo, Juonala, & Raitakari, 2006).

PARTICIPANTS

Recruitment of study participants employed several strategies including email, flyers, and in-person presentations. The study eligibility criteria were adult men and women between the age of 30-65 years old, perform less than 150 minutes of moderate or vigorous physical activity per week, have not used prescription cholesterol or blood pressure medication in the last 3 months, be willing to stop taking any dietary supplements during the study period of 90 days, not pregnant nor planning on getting pregnant during the study, and an APG type of D, E, F or G and/or an HDL-cholesterol to total cholesterol ratio of ≤ 24 percent.

Participants were stratified (male/female) and randomized (block size = 5) to the study treatments using a computer-generated randomization (www.randomizer.org) numbering system.

SAMPLE SIZE

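### Liver and kidney markers are the only stated safety measures, yet none is an entry criterion and no result must be seen before dosing

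*Combined protocol and SAP*

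**What the plan says.** Research Objectives sets out to "assess the safety of the supplement by measuring serum levels of liver and kidney enzymes" and names ALT, AST, LDH (printed there as LHD), BUN and creatinine. No other safety measure appears in the available text. Blood pressure and heart rate are listed as cardiac outcomes.

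Participants lists the entry criteria: age, physical activity, cholesterol or blood pressure medication, willingness to stop supplements, pregnancy, and finally "an APG type of D, E, F or G and/or an HDL-cholesterol to total cholesterol ratio of ≤ 24 percent". None concerns the liver or kidneys, and there is no general medical-history exclusion.

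The introduction describes the product as a mix of amino acids with "vitamins (vitamins A, C, E, folate, vitamin B12), minerals (potassium, magnesium, selenium) and CoQ10". It gives no amounts per serving. Hypotheses says that the 10 g daily serving is the dose on the label.

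Blood Collection says "Blood was drawn at 3 time points in the study": at eligibility, at baseline and after 90 days. It adds: "For eligibility assessment, one 5mL serum tube was withdrawn". Blood Analysis puts total cholesterol, HDL-cholesterol and all five safety markers on one Vitros-350 analyser.

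Statistical Analysis compares arms on the post-treatment value adjusted for baseline. Values beyond the mean ± 3 SD are removed and the results recalculated. The safety markers are not exempted.

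**The concern.** If the five markers matter enough to be the whole safety assessment, it is natural to look at them in each person before dosing. As written, someone with markedly abnormal liver or kidney chemistry meets every entry criterion and can start the product with no requirement that anyone has seen the result. The ingredients make liver and kidney status relevant.

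The second half of the concern is about reporting. A comparison of means answers whether the arms differ on average. Safety also turns on whether any individual moved far out of range. If extreme values are dropped before the means are compared, the values of most interest for safety may not appear in the results at all.

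**Working it through.** The plan has no figure of its own on this point, so most of the check sets its sections side by side.

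**1. Is there a liver or kidney criterion, or a result needed before dosing?** The list in Participants has neither a laboratory limit on the five markers nor a history criterion that could stand in for one. Blood Collection and Blood Analysis contain no step linking dispensing to a result.

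**2. Could the check be done on blood already drawn?** The HDL ratio is one route to entry, so the eligibility tube must be able to yield total and HDL cholesterol. Those two lipids and the five markers share an analyser. The check is therefore feasible if three things hold, none of which the documents state: the Vitros-350 is used at eligibility, the 5 mL volume suffices, and everyone screened gives the tube, including those who qualify on APG type.

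**3. What would it cost?** Inputs from Sample Size: "Overall, 90 adults were screened for eligibility, with 75 adults being deemed eligible".
- Testing only those otherwise eligible: 75 × 5 = 375 assays.
- Testing everyone screened: 90 × 5 = 450 assays.
- In duplicate, as Blood Analysis describes: 2 × 375 = 750, or 2 × 450 = 900.
- Reports to read: 75 to 90.

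**4. Why the limits must be wide.** If each of five independent markers flagged a share q of people, the share flagged on at least one would be 1 − (1 − q)^5. The values of q are assumptions.

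| q per marker | Flagged on any | Of 75 eligible |
|---|---|---|
| 1% | 4.9% | 3.7 |
| 2.5% | 11.9% | 8.9 |
| 5% | 22.6% | 17.0 |

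Correlation between markers would lower these shares. Even so, ordinary reference limits would exclude too many people, so exclusion limits should lie well outside them.

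**5. How many would be excluded with wide limits?** The documents give no rate. Assuming, for illustration, 0.5%, 1% or 2% of people, the expected number among the 75 is 0.4, 0.8 or 1.5.

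**6. Effect on numbers.** The plan takes 60 × 1.2 = 72 to recruit. Sample Size reports: "At the time of starting the study 69 adults chose to participate". The shortfall is 72 − 69 = 3 before any new exclusion. With the plan's 20% attrition, 69 × 0.8 = 55.2, already below 60. Each unreplaced exclusion widens that gap.

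**7. Can the 3 SD rule remove a single extreme safety value?** Take n values of which n − 1 are equal and one lies a distance d away. The mean shifts by d/n, the SD is d/√n, and the odd value stands (n − 1)/√n SDs from the mean, whatever d is. At n = 10 this is 9/3.162 = 2.85; at n = 11 it is 10/3.317 = 3.02. Arm sizes are not given. If the 69 split about evenly, n = 35 gives 34/5.916 = 5.75. Real values scatter, so the figure is lower, but it approaches this limit as the value becomes more extreme. In arms of this size, a sufficiently extreme single value is therefore always removed. If kept, it would move the arm mean by only d/35, about 0.03d.

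**The case against.** The strongest reply is that an outcome need not be an entry criterion. The objective is a between-group comparison, for which baseline and day-90 samples with a placebo arm suffice. The product is a dietary supplement at its labelled dose, and Study Design reports ethics board approval. The available text is also incomplete: an opening part and the consent pages were removed, and a health-history exclusion or a warning to participants could sit there. Recruitment is finished, so an entry check cannot help this cohort. Excluding people with abnormal chemistry would also narrow the population that the safety objective covers.

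Much of this stands. It keeps the severity low and confines the entry check to a repeat trial. It does not remove the point. The list in Participants reads as complete, and neither label dosing nor ethics approval shows that people with liver or kidney disease are safe on the product. Study Design itself cites missing evidence on safety as a reason for the trial. The reporting request needs only existing data.

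A reader might infer that safety results came too late because samples were frozen for later analysis. The text does not support that. The freezing sentence does not separate eligibility from baseline samples, and it does not say when the chemistry was run.

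**Conclusion.** The point holds as a low-severity precaution. In the available text the five markers are the only safety measures, no liver or kidney criterion governs entry, and no result must be seen before dosing. The group comparison is not made wrong by this.

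Two further readings go beyond the documents. One is that the product endangers people with abnormal chemistry; no ingredient amounts are given and no hazard is shown. The other is that such people were probably enrolled; no rate is given, and with limits set well beyond the reference ranges the number would probably be very small.

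The part that can be acted on now is the listing of individual values. Means compared after removal beyond 3 SD can hide the very values that matter for safety. This assumes that the removal rule was applied to the safety markers, as the general wording of Statistical Analysis implies.

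**What to change.** **This completed trial.** Report when the safety chemistry was run. List individual abnormal baseline and day-90 values of the five markers by arm, including any value that the mean ± 3 SD rule removed. This needs only existing data.

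**A repeat trial.** Run the five markers on the existing 5 mL eligibility tube alongside the entry lipids. Require a named role to review them against prespecified clinical exclusion limits, set by the sponsor's clinicians well beyond the reference ranges, before product is dispensed. State that the 3 SD rule does not apply to safety markers.

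**Cost.** The assays and report reading counted above, with no extra draw or visit for those already screened. Any excluded person should be replaced by further screening, because the start was already three below plan. The step does not measure potassium or magnesium.

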and consume it before eating breakfast daily. The group supplementing with Cardioflex ingested one serving (10g) of Cardioflex daily, whereas the placebo group ingested 10g of maltodextrin placebo. We chose this as our placebo supplement because it was likely to have minimal effect on CVD health biomarkers. A log was given to the participants to record their supplement intake. Compliance with the supplement protocol was assessed by measuring blood levels of CoQ10 and providing participants with more treatment packages than the total number of days of the study and asking the participants to return any unused stick packs to the supplement coordinator at the end of the study. We chose blood levels of CoQ10 as our main indicator of compliance because it is not readily found in food and previous research found a significant increase in plasma CoQ10 concentrations when participants were given Coq10 supplements daily (Niklowitz, Sonnenschein, Janetzky, Andler, & Menke, 2007). Thus, it is anticipated that a participant's CoQ10 blood values should increase with Cardioflex supplementation and would indicate compliance with taking the supplement. In addition, participants were given a randomized number of stick packs between 93 and 100, giving every participant at least a few stick packs to return at the end of the clinical trial. Participants were not told the number of stick packs they were given.

Participants were instructed to follow the same diet and maintain the same level of physical activity throughout the clinical trial. To assess dietary intake and physical activity, participants were asked to record everything they ate and drank in a food log and wore a pedometer to track total steps on day 1 (beginning), day 45 (mid-point) and day 90 (end) of the study. A 90-day study length was chosen because previously published data saw significant changes in triglycerides, LDL-cholesterol, HDL-cholesterol, and total cholesterol when participants were given a multi-ingredient supplement for 90 days (Lombardo et al., 2013). A sample size calculation was completed using previously published data (Hobbs et al., 2014) to ensure enough participants were recruited. We calculated that we would need 60 subjects to reach statistical significance. With an expected attrition rate of 20%, we determined that 72 participants needed to be recruited.

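### The recruitment target of 72 does not cover the stated 20% attrition on 60 subjects (75 would), and the value printed as beta is the power

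*Combined protocol and SAP*

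**What the plan says.** The sample-size reasoning appears twice in the combined protocol and SAP.

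- At the end of Study Design, the base number is given as "We calculated that we would need 60 subjects to reach statistical significance", followed by "With an expected attrition rate of 20%, we determined that 72 participants needed to be recruited".
- The Sample Size section repeats 60, 20% and 72 and adds the planning inputs: "With $\alpha = .05$ and $\beta = .90$ and a 12% mean decrease of cholesterol using previously published data". It presents a two-group formula, Equation 1, with a Z term for alpha and a term Z(1−β). The key beneath describes the first only as "constant to the accepted error" and the second as "constant according to power". It defines the standard deviation by symbol and gives no value.

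The calculation is introduced as being "to determine the number of participants needed for the study", which points to 60 being a whole-trial number. No other section changes any of these figures.

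**The concern.** Two statements in one short paragraph disagree with what stands next to them.

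First, the target of 72 is presented as the allowance for losing 20% of participants while needing 60. It adds 20% of the 60, but the loss falls on the larger recruited number, so fewer than 60 would remain at the plan's own attrition rate. The three printed figures (60, 20%, 72) cannot all serve the stated purpose.

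Second, beta is printed as .90, while Equation 1 uses Z(1−β) for power. In the document's own notation that describes a trial planned for 10% power.

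This paragraph is what a reader uses to judge whether the trial was adequately sized. At stake are a small overstatement of the protection against dropout and a wrongly labelled error rate.

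**Working it through.** **Inputs, from Study Design and Sample Size:** evaluable number 60; attrition 20%; recruitment target 72; alpha 0.05 (one- or two-sided not stated); beta printed as .90; no value for the standard deviation.

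**1. Reproducing the plan's target**

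- 60 × (1 + 0.20) = 72. This matches exactly.

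**2. Testing it against its purpose**

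- Remaining after 20% loss: 72 × (1 − 0.20) = 57.6.
- Recruits needed to keep 60: 60/(1 − 0.20) = 75. Check: 75 × 0.80 = 60.
- Shortfall in the target: 75 − 72 = 3.
- Attrition that 72 does cover: 1 − 60/72 = 16.7%.
- With equal arms and rounding up within each arm: 30/0.80 = 37.5, so 38 per arm and 76 in total.

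None of this needs the standard deviation or the sidedness of the test.

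**3. The beta label**

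- Read literally, β = .90 gives Z(1−β) = Z(0.10) = −1.2816. With Z = 1.960 for alpha, the squared term in Equation 1 is (1.960 − 1.2816)² = 0.460.
- Read as power 0.90 (β = 0.10), it is (1.960 + 1.2816)² = 10.51.
- Ratio: 0.460/10.51 = 0.044.

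For 60 in total (30 per arm) to follow from the literal reading with a 12% difference, the standard deviation would have to be about 69% (two-sided). Under power 0.90 it is about 14.3%. The literal reading is not a credible design basis, so .90 is the power.

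**4. Power cost of the attrition slip**

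Assumptions: 60 is the total, 30 per arm, equal arms, giving 90% power; no gain from baseline adjustment. The standardised difference d is solved from Equation 1 with n = 30. Power is then Φ(d√(N/4) − z), where N is the total number of completers and z is the critical value of the test.

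- Planning Z = 1.960: d = √(2 × (1.960 + 1.2816)²/30) = 0.837.
- Planning Z = 1.645: d = √(2 × (1.645 + 1.2816)²/30) = 0.756.

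| Planning Z | Test | Power, N = 60 | Power, N = 57.6 | Loss (points) |
|---|---|---|---|---|
| 1.960 | two-sided | 90.0% | 88.8% | 1.2 |
| 1.645 | one-sided | 90.0% | 88.9% | 1.1 |
| 1.645 | two-sided | 83.3% | 81.8% | 1.5 |

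The third row covers the case where 1.645 was used for planning but the test is two-sided.

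**The case against.** The arithmetic is not in dispute; the case on the other side is about materiality.

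- **The beta label misleads no one.** Equation 1 and its key make the intended meaning clear, and no other number is shown to depend on the label. This stands: it is notation only, and the case for a correction rests mainly on the attrition figure.
- **The slip changed nothing that can be seen.** The document is written after the fact. It reports 75 eligible, 6 who declined and 69 who started, so enrolment fell below 72 as well as 75. This also stands. The 69 are an enrolment result and neither cause nor cure the error; the correction is to the record.
- **Baseline adjustment may absorb the loss.** The primary analysis works by "comparing the two groups, and controlling for their baseline values by using analysis of covariance". If σ in Equation 1 is the standard deviation of the raw outcome, a correlation r between baseline and outcome raises the effective number to 57.6/(1 − r²). At r = 0.2 that is 57.6/0.96 = 60, which cancels the shortfall; at r = 0.3 power would be about 91.5%. Neither r nor the kind of σ is in the documents, so this is possible but unproven. It bears on the consequence and not on whether 72 allows for 20% attrition.
- **The power range depends on how 60 is read.** Equation 1 in its usual form gives a number per group. Had 60 been that number but been used as the total, two-sided power would be about 63.0% at 60 and 61.2% at 57.6, a loss of 1.8 points. The wording, and the fact that 72 is the whole-trial target built on 60, favour reading 60 as the total, but the documents do not spell it out. Equal arms are likewise an assumption: the Participants section gives a block size of 5, which cannot split evenly between two treatments.
- **Equal arms would need 76, not 75.** True, but this only widens the gap.

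**Conclusion.** The concern holds, at minor severity. On the plan's own figures, 72 recruits do not leave 60 after 20% attrition. The target is 3 short of 75 as a total and covers 16.7%. That conclusion rests on no assumption beyond the printed numbers.

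The beta of .90 is a mislabelled power. It should be corrected, but it is not evidence against the 60.

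The cost in power is 1.1 to 1.5 percentage points whichever Z was used. That range is conditional on 60 being the total in equal arms at the planned 90% power, and it ignores any gain from the covariate adjustment. The 60 itself cannot be checked from the documents, because neither the standard deviation nor the sidedness is given.

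**What to change.** 1. In Sample Size, replace the beta statement with power = 0.90 (beta = 0.10).
2. In both Study Design and Sample Size, keep 72 as the target actually used, and add either that 20% attrition on 60 requires 75, or that 72 covers attrition of 16.7%.
3. As a clarification and not a correction, state in the same place the standard deviation used, the Z value for alpha (one- or two-sided), and that 60 is the total across both arms, if the authors confirm it. The base figure can then be reproduced.

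The cost is wording in two sections. It requires no additional participants and no change to the analysis.
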